**2 STUDY OBJECTIVES AND ENDPOINTS**

| Primary Objectives:   | Primary Endpoints:  |
|--|--|
| To characterize the safety of topical OTT166 in participants with DR   | 
 
• Proportion of participants who develop treatment-emergent adverse events (TEAEs) through Week 24
 
   |
| To characterize the efficacy of topical OTT166 in participants with DR   | 
 
• Proportion of participants who have improved by <math>\geq 2</math> steps from baseline at Week 24 as determined by central reading center assessment using the DRSS
 
   |
| Secondary Objectives:   | Secondary Endpoints:  |
| To determine if topical OTT166 will prevent or delay the occurrence of visually threatening complications (VTC), defined as PDR worse than mild and/or anterior segment neovascularization (ASNV) determined by the investigator and/or CI-DME (defined below) | 
 
• Proportion of participants developing worse than mild PDR (DRSS 65 and above) at Week 24
 
• Time to development of PDR worse than mild (DRSS 65 and above)
 
• Proportion of participants who develop ASNV determined by the investigator at Week 24
 
• Proportion of participants who develop VTC at Week 24
 
• Time to development of PDR worse than mild (DRSS 65 and above) or CI-DME
 
 |

# Parexel International

OcuTerra Therapeutics, Inc.  
OTT166-201

Statistical Analysis Plan

|  |   |
|--|---|
| 
To determine if topical OTT166 will prevent or delay the occurrence of CI-DME (CI-DME is defined as the presence of fluid in the central subfield in participants who have no fluid at baseline or CST > 325 μm)
 | 
 
• Proportion of participants who develop CI-DME at Week 24
 
• Time to development of CI-DME
 
   |
| 
To determine the effect of OTT166 on DRSS in participants with moderately severe to severe NPDR and mild PDR treated with topical OTT166
  | 
 
• Proportion of participants with change in DRSS steps at Week 24 compared to baseline                         
 
– Change in DRSS steps is defined as DR worsening or improving by 1, 2, or ≥ 3 steps.
 
 
 
• Proportion of participants with mild PDR (DRSS score 61B) at baseline who regress to NPDR (DRSS score ≤ 53) by Week 24
 
 |
| 
To determine the effect of OTT166 on BCVA in participants with moderately severe to severe NPDR and mild PDR
  | 
 
• Mean and median change in BCVA (ETDRS letters) from baseline to Week 24
 
• Lines gained/lost in BCVA (± 5, 10, and 15 ETDRS letters) at Week 24
 
• Mean and median change in area under the curve (AUC) for change in BCVA from baseline to Week 24
 
   |
| 
To determine the effect of OTT166 on central subfield thickness in participants with moderately severe to severe NPDR and mild PDR
  | 
 
• Mean and median change in CST from baseline to Week 24
 
• AUC for change in CST from baseline to 24 weeks
 
   |
| 
To determine the effect of OTT166 on the need for rescue therapy in participants with moderately severe to severe NPDR and mild PDR
   | 
 
• Proportion of participants who met the objective rescue criteria as defined in protocol Section 2.14.9.
 
• Time to meet objective rescue therapy criteria as defined in protocol Section 2.14.9.
 
  |
| 
Exploratory Objectives
   | 
Exploratory Endpoints
   |
| 
To evaluate the change in DME in participants treated with OTT166
   | 
 
• Change in Macular Volume (MV) from baseline to Week 24 for 1-, 3-, and 6-mm regions
 
   |

|  |  |
|--|--|
| 
To assess the effects of treatment on anatomic markers other than DRSS and on retinal non-perfusion
 | 
 
• Change in area of retinal non-perfusion from baseline to Week 24 seen on widefield fluorescein angiography (FA)
 
• Proportion of participants with intact foveal avascular zone (FAZ) seen on widefield FA at Week 24
 
• Optical coherence tomography angiography (OCTA) endpoints within the 6 mm area:             
 
- Change from baseline to Week 24 in FAZ area
 
- Change from baseline to Week 24 in non-perfusion area
 
- Change from baseline to Week 24 in vessel caliber
 
- Ischemic Index at Week 24 compared to baseline
 
- Proportion of participants with new neovascularization at Week 24
 
- Proportion of participants with new intraretinal microvascular abnormality (IRMA) at Week 24
 
- Change in vessel density from baseline to Week 24 in the superficial and deep layers
 
 
 
 |
|--|--|

**3 INVESTIGATIONAL PLAN**

**3.1 Overall Study Design and Plan**

This is a Phase 2 randomized, double-masked, vehicle-controlled, multicenter study to evaluate the safety and efficacy of OTT166 ophthalmic solution in the treatment of DR. The OTT166 201 Phase 2 will be conducted to select an optimum dosing regimen (frequency) for Phase 3 pivotal trials.

The study population will be participants with Type 1 or Type 2 diabetes under adequate control as evidenced by glycosylated hemoglobin ( $HbA1c \leq 12.0\%$ ), who show typical fundus alterations and have been diagnosed with moderately severe to severe NPDR or mild PDR, as defined by the DRSS Steps 47, 53 and 61B ([Appendix 6.2](#)). Participants may have fluid in the macula with BCVA of  $\geq 69$  Early Treatment Diabetic Retinopathy Study (ETDRS) letters (Snellen equivalent 20/40) and Central Subfield Thickness (CST) of  $\leq 325 \mu m$ , and a normal foveal contour, which needs to be confirmed by an independent central reading center, in at least 1 eye.

Approximately 210 participants diagnosed with moderately severe to severe NPDR or mild PDR and who are treatment naïve (*i.e.*, no prior anti-Vascular Endothelial Growth Factor [VEGF] or laser (focal, grid, Pan-Retinal Photocoagulation [PRP]) administered) will be randomized 2:2:1:1 into the following groups: OTT166 5% BID, OTT166 5% QID, vehicle control 5% BID, vehicle control 5% QID. Randomization will be stratified by Screening DRSS score (47 or 53 or 61B). Participants with PDR (DRSS score 61B) will be capped at 20% of all randomized participants. 5% OTT166

ophthalmic solution or vehicle control, will be given to the participants who will self-administer one 50-microliter eye drop of study solution at the prescribed frequency based on randomization, for 24 weeks.

Eyedropper bottles containing active treatment of OTT166, and corresponding vehicle control are identical in appearance (size, color, shape) and associated with a unique number. Eye dropper bottles will be dispensed at the study visits summarized in the schedule of activities (SoA) in [Appendix 6.1](#).

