2 STUDY PROTOCOL

2.1 Study Rationale

This study is designed to provide proof -of -concept that NPDR and mild PDR can be effectively treated with a topical eye drop formulation of OTT166. Furthermore, this study is designed to determine the dose-exposure response of OTT166 in terms of efficacy and safety in order to support the dose selection for the subsequent pivotal Phase 3 studies with OTT166 in DR.

OTT166 is a representative from a new class of drugs (ie, a topical integrin inhibitor targeted to the back of the eye). It is being developed for treatment of DR. The study is intended to show in particular that OTT166:

- Is overall safe and well tolerated
- Prevents progression of DR
- Prevents VTCs and/or CI-DME
- Reverses retinal changes attributed to DR
- Maintains visual acuity

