**1 INTRODUCTION**

OTT166 is a representative from a new class of drugs, i.e., a topical integrin inhibitor targeted to the back of the eye. It is being developed for treatment of Diabetic Retinopathy (DR). This study is designed to provide the proof of concept that non-proliferative diabetic retinopathy (NPDR) and mild proliferative diabetic retinopathy (PDR) can be effectively treated with a topical eye drop formulation of OTT166. Furthermore, this study is designed to determine the dose-exposure response of OTT166 in terms of efficacy and safety in order to support the dose selection for the subsequent pivotal Phase 3 studies with OTT166 in DR.

This Statistical Analysis Plan (SAP) describes all planned analyses for the Clinical Study Report (CSR) of Phase 2 Randomized, Double-Masked, Vehicle-Controlled, Multicenter Study to Evaluate the Safety and Efficacy of OTT166 Ophthalmic Solution in the Treatment of DR.

The structure and content of the SAP are based upon the International Conference on Harmonisation (ICH) E3 – Guideline for Industry Structure and Content of Clinical Study Reports.

The content of this SAP is based on following study document:

- Study Protocol Version 5.0 dated October 10, 2023.

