## 4.10 Efficacy Evaluation

### 4.10.1 Analysis and Data Conventions

This study is designed to evaluate the superiority of two doses of OTT166 (5 mg/day and 10 mg/day) compared to vehicle control for the treatment of DR. For each dose within each endpoint, the null hypothesis is that there is no difference between OTT166 and vehicle control or the difference is in the direction of inferiority of OTT166, and the alternative hypothesis is that there is a difference between OTT166 and vehicle control in the direction of superiority of OTT166.

All statistical tests will be one-sided and will be performed at the 5% level of significance, unless otherwise stated. The vehicle control group will be combined for all efficacy analyses and two-sided 90% confidence intervals will be presented. A comparison between the two control groups will be performed for the primary endpoint to confirm the groups are comparable.

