#### 4.10.2 Primary Efficacy Analysis

The primary efficacy outcome measure of the study will be the proportion of participants who have improved by  $\geq 2$  steps from BL DRSS at Week 24. DRSS score levels will be recoded into 12 steps, provided by WRC.

Comparison of the primary endpoint will be made between each dose group and the combined vehicle control group using Mantel-Haenszel (MH) test of the difference in two proportions stratified by the randomization stratification factor (BL DRSS score 47 or 53 or 61B). The estimated MH risk difference will be summarized along with the two-sided 90% CI using MH stratum weights and the Sato variance estimator.

The primary efficacy analysis will be performed on the ITT Analysis Set, while the PPS will be used as a supplementary analysis. ICEs and missing data will be handled as described in [Section 4.10.1.2](#).

In order to assess the robustness of the study conclusions to the choice of imputation method, the following sensitivity analyses will be performed on the ITT Analysis Set and PPS for the primary endpoint:

- An observed case analysis where only observed responses will be used for analysis.  
Observed data after initiation of rescue medication will be set to missing.
- A LOCF analysis where missing post-baseline responses will be imputed using the LOCF procedure.  
Measurements after rescue will be imputed using the last observation prior to rescue treatment; a non-response will be imputed if no post-baseline measurements are available.

A supplementary analysis will be performed on the ITT Analysis Set and PPS for the primary endpoint to assess the time to improvement of  $\geq 2$  steps improvement from BL in DRSS score. Analyses will be based on observed data, where participants who receive rescue medication will be censored at the start of rescue medication (unless improvement of  $\geq 2$  steps improvement from BL in DRSS score is achieved prior to starting rescue medication). This analysis will be presented based on the Kaplan-Meier method, along with a 90% confidence interval. A stratified log-rank test adjusting for the randomization stratification factor will be performed, to compare the combined vehicle control with each treatment group. Additionally, a stratified Cox proportional hazards model adjusting for the randomization stratification factor will be employed to estimate the hazards ratio between the combined vehicle control and each treatment group.

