#### 4.13 Determination of Sample Size

The study will enroll approximately 210 participants, 70 participants in each OTT166 treatment group and 35 participants per group into each matching vehicle control group and allowing for around 5% study attrition, this will ensure at least 66 participants per treatment group and combined vehicle control group.

For the primary endpoint of improvement by at least 2 steps from baseline on the DRSS at Week 24, completing 66 participants per group (active treatment BID, active treatment QID, combined vehicle control) through Week 24 will yield at least 90% power to demonstrate that the active treatment is superior to placebo using a 1-sided alpha of 0.05, provided that the true treatment effect (active treatment efficacy rate minus control efficacy rate) is at least 0.20 and the control efficacy rate is at most 0.06.

The sample size calculation was computed in nQuery 8.7 using a Chi square test for two proportions (continuity corrected).

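### The trial is run to choose a dosing frequency, but no planned efficacy analysis estimates the difference between active QID and active BID or its uncertainty

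*SAP*

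**What the plan says.** Choosing the frequency is the declared reason for the trial. SAP 3.1 says: "The OTT166 201 Phase 2 will be conducted to select an optimum dosing regimen (frequency) for Phase 3 pivotal trials". The Protocol synopsis and section 2.6 say the same. Protocol 2.1 adds that "this study is designed to determine the dose-exposure response of OTT166 in terms of efficacy and safety", and the SAP introduction ties this to Phase 3 dose selection.

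The planned contrasts are these:

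- **Primary endpoint (SAP 4.10.2):** "Comparison of the primary endpoint will be made between each dose group and the combined vehicle control group", by a stratified MH test, with the MH risk difference and a Sato two-sided 90% CI. The population-level summary of the primary estimand (SAP 3.2.2) is the same contrast.
- **Hypotheses (SAP 4.10.1):** each dose is set against vehicle. "All statistical tests will be one-sided and will be performed at the 5% level of significance, unless otherwise stated".
- **Secondary and exploratory endpoints (SAP 4.10.3, 4.10.4):** ANCOVA, log-rank and Cox contrasts are each dose against combined vehicle. The proportional odds model has treatment group as a covariate but names no QID-BID contrast.
- **Other comparisons:** SAP 4.10.1 compares the two vehicle groups with each other on the primary endpoint. SAP 4.10.4 compares the two eyes of participants in the active groups. Neither compares active QID with active BID.
- **Safety, exposure and compliance:** summarised by arm, with no inferential statistics for safety (SAP 4.9, 4.11).

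Neither document contains a QID minus BID estimate, an interval for it, a dose-response model or a rule for choosing the frequency.

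**The concern.** The decision the trial is meant to inform is a comparison of two active regimens. The inferential efficacy output consists of two comparisons with a shared vehicle group. Each answers whether that regimen beats vehicle; neither says how far apart the regimens are or how well that gap is known.

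Two misreadings become easy. One regimen may reach p<0.05 and the other not, and this may be taken as a difference between them when chance explains it. Or both may reach p<0.05 and be taken as equivalent when one is better. An interval for the difference guards against both. A contrast first run after unmasking would be post hoc.

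**Working it through.** **Inputs from the documents.** SAP 4.13: 66 completers per group (BID, QID, combined vehicle), one-sided alpha 0.05, continuity-corrected chi-square, around 5% attrition. The claim is that follow-up "through Week 24 will yield at least 90% power to demonstrate that the active treatment is superior to placebo" if the effect "is at least 0.20 and the control efficacy rate is at most 0.06". Hence the planning rates are 0.26 and 0.06.

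**Step 1. Reproduce the stated sample size.** The mean rate is 0.16.

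Uncorrected n = [1.645·√(2·0.16·0.84) + 1.282·√(0.26·0.74 + 0.06·0.94)]² / 0.20² = (0.853 + 0.639)² / 0.04 ≈ 55.7, so 56.

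Continuity-corrected n = (56/4)·[1 + √(1 + 4/(56·0.20))]² ≈ 65.6, so 66 per group.

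Power at 66 is 90.3%. Attrition gives 66/0.95 = 69.5, so 70 per group and 210 in all. The plan's figure is correct, and it concerns active against vehicle only.

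**Step 2. What the two vehicle tests say about the regimens.** Exact binomial enumeration, 66 per group, shared vehicle at 6%, pooled z test at one-sided 0.05, unstratified, no imputation. Only the 26% and 6% rates come from the plan; 20%, 16% and 36% are assumptions used to show a range.

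| True BID | True QID | Both significant | Exactly one | Neither |
|---|---|---|---|---|
| 26% | 26% | 91.6% | 7.4% | 1.0% |
| 20% (assumed) | 20% (assumed) | 68.3% | 23.4% | 8.3% |
| 16% (assumed) | 16% (assumed) | 43.1% | 32.5% | 24.4% |
| 26% | 36% (assumed) | 95.2% | 4.7% | 0.1% |

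In the first three rows the regimens are identical, so every split result is chance. In the last row QID is 10 points better, and the tests agree with each other about 95% of the time.

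**Step 3. Side-by-side rates are not enough.** With both true rates at 26%, the observed rates differ by 10 points or more in about 20% of trials.

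**Step 4. The missing interval.** The 90% half-width for QID minus BID, both at 26%, is 1.645·√(2·0.26·0.74/66) = 0.126. At 26% and 36% it is 1.645·√((0.26·0.74 + 0.36·0.64)/66) = 0.132.

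**Step 5. It cannot be rebuilt from the two planned intervals.** Each vehicle-referenced difference has variance (0.26·0.74 + 0.06·0.94)/66. Treating the two as independent gives a half-width of 1.645·√(2·(0.26·0.74 + 0.06·0.94)/66) = 0.143. That counts the shared vehicle group twice, although it cancels from the contrast. The planned analysis also pools stratified estimates over 100 imputations, which a reader of the tables cannot repeat.

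**The case against.** A reader might infer that the frequency will be chosen by which p-value crosses 5%. The documents do not say so. SAP 3.2.2 says only that the dose-versus-vehicle question will support dose selection. By arm, the sponsor will also have risk differences with 90% CIs, by-visit summaries, Kaplan-Meier estimates and hazard ratios, adverse event tables, and overall and monthly compliance. This objection stands: the gap is a missing estimate of the difference, not a faulty selection rule.

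A reader might also infer that the trial is undersized or cannot inform the choice. That is not supported either. The sample size reproduces, and a Phase 2 trial need not be powered for dose against dose. At 66 per arm, a one-sided 5% test would have about 34% power for 26% vs 36%. Subtracting the two reported risk differences already gives roughly the point estimate, so what is lacking is mainly the pre-specified contrast and its uncertainty.

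Two further objections limit the size of the point. At the planning rates a split result occurs in only 7% of trials; the larger figures depend on assumed smaller effects. And the added interval would seldom settle the matter: by exact enumeration of an unstratified Wald 90% CI, it excludes zero in about 10% of trials when both rates are 26%, and in about 36% when the rates are 26% and 36%. Both objections are correct. The interval is worth having because it shows how little the trial can separate the regimens, not because it will decide between them.

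**Conclusion.** The point holds as a gap in the analysis plan. The stated purpose is to select a frequency, and no planned efficacy analysis gives the active QID minus active BID difference with its uncertainty. The validity of the vehicle comparisons and the stated power are unaffected.

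The risk of a misleading split between truly equal regimens is modest at the plan's rates and about a quarter to a third of trials under the assumed weaker effects. The opposite failure, no separation despite a real 10-point advantage, would be the usual result. These figures assume 66 per group and ignore stratification and imputation. The change is worth making before unmasking because it needs no new data, model or participants.

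**What to change.** - **SAP 4.10.2:** add the stratified MH risk difference, QID minus BID, with the Sato two-sided 90% CI, on the ITT Analysis Set. Use the same intercurrent-event handling and the same imputed data sets.
- **SAP 4.10.3:** take the same contrast, with a two-sided 90% CI, from the existing ANCOVA models for BCVA and CST.
- **Labelling:** mark these results as estimation only, with no hypothesis test and no alpha spent. State that a difference in significance against vehicle will not be interpreted as a difference between regimens.

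The cost is about one extra row per affected efficacy table. The downside is a wide interval, about ±12.6 points if both rates are 26%, which will often leave the choice open. The change does not say which frequency to select or how the sponsor should weigh efficacy, safety and compliance; that remains the sponsor's decision.

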**3.2 Endpoints**

**3.2.1 Primary Endpoint - Safety**

The primary safety outcome measure of the study will be the proportion of participants who develop TEAEs through Week 24.

**3.2.2 Primary Efficacy Endpoint and Estimand**

The primary efficacy outcome measure of the study will be the proportion of participants who have improved by  $\geq 2$  steps from baseline at Week 24 as determined by central reading center assessment using the DRSS. The primary clinical question of interest is to determine the effectiveness of different doses of OCT166 versus vehicle control on  $\geq 2$  steps improvement from BL in DRSS score at Week 24 without requiring rescue treatment if the study drug is not discontinued prior to Week 24. This will support the dose selection for subsequent pivotal studies of OTT166. The estimand for the primary efficacy analysis is defined as follows:

|   | Primary Estimand  |
|---|--|
| Treatment conditions of interest | OTT166 5 mg/day, OTT166 10 mg/day and matching vehicle control   |
| Participant Population           | DR participants with Type 1 or Type 2 diabetes under adequate control (HbA1c $\leq 12.0\%$ ) who show typical fundus alterations and have been diagnosed with moderately severe to severe NPDR or mild PDR as defined by the DRSS Steps 47, 53, and 61B, with BCVA $\geq 69$ ETDRS letters, CST of $\leq 325 \mu\text{m}$ , and a normal foveal contour. |
| Endpoint                         | $\geq 2$ steps improvement from BL in DRSS score at Week 24  |
| Population level summary         | Difference in proportion of participants achieving $\geq 2$ steps improvement from BL in DRSS score at Week 24 between each OTT166 treatment group and the combined vehicle control group.   |

|   | Primary Estimand  |
|---|--|
| Intercurrent events (ICEs) and strategies to handle ICEs | 
a) Rescue treatment in the study eye due to worsening DRSS level to 65 or higher prior to assessment of DRSS at Week 24
Composite strategy (non-response)
 
b) Death prior to DRSS assessment at Week 24
Hypothetical strategy
 
c) Use of rescue treatment in the study eye for any other reason prior to DRSS assessment at Week 24
Composite strategy (non-response)
 
d) Premature discontinuation of study drug for any reason prior to DRSS assessment at Week 24
Hypothetical strategy
 
e) Study drug compliance <75% through Week 24
Treatment policy strategy
 
f) Study drug compliance between 75% to <90% through Week 24
Treatment policy strategy
 |
|   | ICE(s) with a composite variable strategy take priority over ICEs with other strategies. And ICEs with a hypothetical strategy take priority over ICEs with treatment policy strategy.   |

A Supplemental Estimand will be defined and analyzed where the ICEs defined above will be handled using alternative strategies as follows: c and e are changed to Hypothetical strategy.

